The primary purpose of this randomized controlled trial is to determine if patient self-matching to psychotherapy treatment methods improves 1) drinking outcome, 2) compliance and 3) quality of life for patients being treated for alcohol problems compared to assignment as usual, which is by the means of expert matching.

A priori hypotheses

1. Patients who choose their own treatment will show significantly greater reductions in alcohol consumption (measured by number of days with excessive drinking) at follow-up, when compared to patients assigned to treatment by expert match.
2. Patients who choose their own treatment method will show significantly better compliance in treatment (measured by retention) when compared to patients assigned to a specific treatment method by expert match.

Material and methods

Study Design

The study is conducted as a superiority randomized controlled trial. 401 consecutive patients aged 18 or more are enrolled. All new patients fulfilling the inclusion criteria receive oral and written information about the study. Patients are randomized to either expert matching (algorithm) or self-matching. See the study protocol for more information on referral routines[13].

Study procedures

Information about the study is presented when the potential participant first attends the treatment center. If the patient needs treatment for withdrawal symptoms, the information is not given until those symptoms are sufficiently treated.

The baseline interview is divided into two sessions to avoid fatigue during a long assessment. This is already standard procedure in the clinic for everyone receiving treatment regardless of participation in this study. Upon written and oral

consent patients are randomized to either choosing their own treatment among five options or being assigned to one of these options by means of an algorithm[14] and expert opinion. Patients participating in the study will be re-interviewed 6 months after initiation of treatment.

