Getting patients to participate in studies and getting a high follow-up rate is usually an obstacle in research, thus we have designed the study routines as similar as possible to the usual assessment routines in the participating treatment institution. The only difference for those participating in this study is the 45-minute follow-up interview. To ensure a high follow-up rate we collect phone number, e-mail and home address on patients and their next of kin. If patients decide to be anonymous, we underline the importance of their responsibility to contact the treatment center 6 months after treatment start.

Randomization and blinding

Patients are assigned to conditions by REDCap (Research Electronic Data Capture) from Open (Odense Patient Data Explorative Network), a computer-based randomization system. The interviewer in charge of the first baseline interview will activate the randomization, when the patient has agreed to participate in the study. The patient witness' the randomization and the result are revealed immediately.

A case report for each participant will be prepared and labeled with participant number. All case reports will be stored in a locked storage inaccessible to the therapists, who are to remain uninformed of how patients were assigned to treatment. Patients are urged not to reveal their group assignment.

Data

The following instruments will be administered to provide standardized measures of alcohol problems, quality of life and personality traits:

- Addiction Severity Index (ASI) is an assessment tool for addiction problems [15].
- Time Line Follow Back (TLFB) is an assessment tool for measuring drinking days the last 30 days [16].
- WHO quality of life 26-item questionnaire (WHOQOL-BREF) [17].

- NEO Five-Factor inventory-3 (NEO-FFI-3) is a tool for measuring personality traits [18].
- Personal Happiness Form (PHF) is a tool for assessing well-being [19].

These validated and widely-used instruments will allow direct comparisons with mainstream clinical trials.

Statistical analyses and sample size

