A multiple regression model will be used to model percent of days with drinking/excessive drinking. If the model validation shows that Gaussian multiple regression does not fit due to severely non-normal data, a multiple quantile regression model will be used instead. Both modeling approaches allow for inclusion of additional explanatory variables. A two-sided alternative will be used with a significance level of $p=0.05$. We expect that proportion of patients assigned to the five treatments will differ between the two groups; hence, type of treatment, sociodemographic data and problem severity will be integrated in the analysis as explanatory variables.

Power calculation

To our knowledge no similar experimental studies have been conducted. The power calculation is therefore estimated from what clinicians' regard to be a clinically meaningful difference in outcome. A study by Miller and Manuel [20] found that clinicians estimated the difference between two treatment methods to be meaningful for implementation in daily practice if the continuous outcome measures (e. g. number of days with excessive drinking) were halved. The power calculation is based on the number of days with excessive alcohol abuse over the last 30 days after 6 months of treatment.

Currently, patients at the participating outpatient clinic drink on average excessively 5.7 days ($SD=9.7$) over the last 30 days after 12 months of treatment. With the new methods for assigning treatment to patients, we seek to halve the number of days with excessive drinking to an average of $5.7/2 = 2.85$ days, i.e. a reduction of 2.85 days. We assume the standard deviation will be the same for the reduced number of days. Most likely, it will be smaller since less than zero days of excessive drinking is impossible, i.e. the method is conservative. As stated by Miller & Manuel [20] this power calculation is based on practitioners' judgment of a meaningful difference in outcome, rather than statistical significance based on other studies. By this approach, a total sample of 200 patients in each group is needed to have 90% power of detection a difference of this magnitude using a 0.05% level of statistical significance (Figure 2).

Sensitivity analyses

Complete case and worst-case computation will be carried out.

Interim analyses and stopping rule

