An Independent Data Monitoring Board was assigned to carry out interim analyses. In case of significant and clinically relevant difference the study will be terminated due to ethical responsibility to provide the best treatment possible.

Start of data analyses

Data analyses will start primo January 2020.

Level of confidence and *p* values

A confidence level of 95% and *p* value of 0.05 is assigned.

Missing data

Incomplete follow-up data are assumed to be missing at random (MAR) and will be addressed by the MICE (multivariate imputation by chained equations) method of multiple multivariate imputation. Appropriate auxiliary variables will be included in the imputation model, the resulting datasets will be analyzed separately, and results will be combined using the rules of Rubin.

Outcome measures

For each outcome measure, two analyses will be carried out:

1. Intention-to-treat analyses (ITT) will be carried out on all patients, irrespective of whether they completed the interventions or were re-interviewed. Regarding incomplete data, multiple imputations is used together with ITT but there will be some caveats.
2. Completer (on-treatment) analyses will be carried out on patients who completed the respective interventions.

Results will be published regardless of our findings.

Primary outcome:

Number of excessive drinking days 6 months after initiation of treatment.

Secondary Outcomes:

1. Compliance measured by retention. At 6 months follow up the number of sessions attended is measured.

2. The four dimensions of Quality of life as measured by WHOQOL.

Table 1. Demographics and baseline data.

	Self-Match	Expert match (TAU)	Significance level
Demographics			
Current age mean (SD)			
Male			
Currently cohabiting or married			
Full or part time employment			
Annual income Mean (SD)			
Education (>high school)			
Treatment related to AUD and substance use			
Previously received AUD treatment			
Previously received SUD treatment			
Currently suffering from SUD			
Use of alcohol			
Number of heavy drinking days last 30 days			
Number of drinking days last 30 days			
Overall amount of alcohol consumption last 30 days			
Quality of Life			
Physical domain (sum score)			
Psychological domain (sum score)			
Social domain (sum score)			
Environment domain (sum score)			

Table 2. Follow up data

	Self-Match group	Control Group	Significance level
Follow up rate			
Percentage completed follow up			
Drinking outcome			
Heavy drinking days last 30 days			

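### The 200 per group is a count of observed 6-month outcomes with no allowance for missing ones, so the stated 90% power does not describe the trial as enrolled

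*SAP*

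**What the plan says.** Under Power calculation, the SAP takes as its starting point that patients at the clinic "drink on average excessively 5.7 days ($SD=9.7$) over the last 30 days after 12 months of treatment". It aims to halve that mean to 2.85 days, keeps the SD at 9.7 in both arms, and concludes that "a total sample of 200 patients in each group is needed" for "90% power of detection a difference of this magnitude". No follow-up rate or inflation for losses enters the calculation. Statistical analyses and sample size specifies a two-sided test at 0.05.

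Study Design states that "401 consecutive patients aged 18 or more are enrolled".

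Other sections prepare for missing outcomes:

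- Study procedures remarks that "getting a high follow-up rate is usually an obstacle in research". It describes contact details collected to counter this, and relies on anonymous patients to contact the centre themselves at 6 months.
- Missing data says "Incomplete follow-up data are assumed to be missing at random (MAR") and plans multiple imputation by chained equations with auxiliary variables.
- Outcome measures keeps patients who were not re-interviewed in the intention-to-treat analysis.
- Sensitivity analyses plans complete-case and worst-case computations, and Table 2 has rows for follow-up.

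**The concern.** A sample size formula of this kind returns the number of outcome values that must be observed. Here that number was used as the number to enrol, in a plan that expects some outcomes to be missing. If so, the 90% belongs to a trial with complete follow-up. The primary comparison would then be less sensitive than stated, and a null result reported alongside a 90% power claim would look like stronger evidence of no difference than it is.

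**Working it through.** **Inputs.** Difference 2.85 days, SD 9.7 in both arms, 200 per group and 90% power (Power calculation); two-sided 0.05 (Statistical analyses and sample size); 401 enrolled (Study Design). The power sentence prints "using a 0.05% level of statistical significance". This is read as 5%, because a literal 0.0005 would need 485 (one-sided) or 526 (two-sided) per group. The loss rate is not in the SAP; 10%, 20% and 30%, equal in both arms, are assumptions. The split of the 401 is not given and is taken as 200 per arm.

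**Step 1: reproduce the 200.** n per group = 2 × SD² × (z_alpha + z_power)² / difference².

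- One-sided 5%: 2 × 9.7² × (1.645 + 1.282)² / 2.85² = 198.4, so 199 (200 with the t-test).
- Two-sided 5%: 2 × 9.7² × (1.960 + 1.282)² / 2.85² = 243.4, so 244 (245 with the t-test).

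The 200 is therefore the one-sided requirement with all outcomes observed, and nothing is left over as an attrition margin. Enrolment of 401 is 2 × 200 + 1, so there is no reserve there either.

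**Step 2: separate sidedness from attrition.** With 200 observed per group, SE = √(2 × 9.7² / 200) = 0.97 and 2.85 / 0.97 = 2.94. The t-test has power 90.1% one-sided and 83.4% two-sided. That drop is due to sidedness alone.

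**Step 3: add missing outcomes.** Observed n per group = 200 × (1 − loss), SE = √((SD₁² + SD₂²) / n), with power from the noncentral t. This is an unadjusted complete-case comparison.

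The second SD column below uses a ceiling. On a 0–30 day scale with mean 2.85, the SD cannot exceed √(2.85 × 27.15) = 8.80. The plan's 9.7 is therefore not attainable in the self-match arm if that arm reaches its target mean.

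| Assumed loss | n per group | Two-sided, SD 9.7/9.7 | Two-sided, SD 9.7/8.8 | One-sided, SD 9.7/9.7 |
|---|---|---|---|---|
| 0% | 200 | 83% | 87% | 90% |
| 10% | 180 | 79% | 83% | 87% |
| 20% | 160 | 75% | 78% | 84% |
| 30% | 140 | 69% | 73% | 79% |

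The last column isolates attrition on the basis that yields 200: about 3, 6 and 11 points lost.

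**Step 4: what imputation can return.** Suppose auxiliary variables explain a share R² of the outcome variance. To a large-sample approximation, the variance of an arm mean is then SD² × [(1 − R²)/n_observed + R²/n_randomised]. At 20% loss and an assumed R² of 0.25, the bracket is 0.75/160 + 0.25/200 = 0.00594, equivalent to about 168 patients. At R² = 0.50 it is 0.50/160 + 0.50/200 = 0.00563, about 178 patients. With SD 9.7 in both arms, two-sided power is about 77% and 79%. For the unadjusted comparison, imputation cannot lift power above its no-loss value of 83%.

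**The case against.** **This is an omission, and the protocol may cover it.** The sentence does not claim that 90% survives losses, the SAP cites a protocol that is not at hand, and Figure 2 is not visible. But the SAP prints the whole calculation and its result. Since 200 matches the zero-loss formula, neither source can put an attrition margin into it.

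**Most of the visible gap is sidedness.** This stands in part. The fall from 90% to 83% has nothing to do with attrition and exceeds what a 10% loss adds (83% to 79%). A reader might credit missing data with the whole distance from 90% to 79% or 69%; the arithmetic does not support that.

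**The SD of 9.7 in both arms is pessimistic.** This stands. The plan itself expects a smaller SD in the improved arm. At the 8.8 ceiling, two-sided power rises by about 3 to 4 points, and as 8.8 is a maximum, that column is a lower bound for a control SD of 9.7. A self-match SD of about 7.8 or less would restore 90% with no loss. The plan does not assume such a value or offer it as an allowance.

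**The planned analysis can gain precision.** This also stands. The regression includes sociodemographic and severity variables. With an assumed R² of 0.2 and SDs 9.7/8.8, power would be about 93% with no loss, 90% at 10% and 87% at 20%. It is therefore tempting but unsupported to say that the trial's real power must be below 90%. The R², like the loss rate, is not in the plan.

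**Follow-up may be good.** The remark on follow-up is a general one and is followed by measures to counter the problem. Nothing in the SAP points to a loss as high as 30%.

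**Little depends on it now.** Restating power changes no estimate, test or analysis set, and confidence intervals are the better guard against over-reading a null result. That limits the weight of the point, but does not make the stated power right.

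**Conclusion.** Wrong as written. The 200 per group is a number of observed outcomes with no attrition allowance, and 401 enrolled leave no reserve, in a plan that provides for incomplete 6-month data. The calculation as printed does not support 90% for the two-sided test. Missing outcomes add to the sidedness shortfall and would remain a fault after that was corrected.

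The size is conditional on an assumed loss. At 10% to 30%, attrition takes two-sided power from 83% down to 79–69% (SD 9.7 in both arms), or from 87% down to 83–73% (self-match SD at its ceiling). These are unadjusted complete-case figures. Auxiliary variables and covariate adjustment may recover part of the loss, by an amount the plan does not quantify. What is established is that the stated 90% lacks support, not that the trial's true power is any one of these values.

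**What to change.** In Power calculation, state that 200 per group means patients with an observed 6-month outcome. Replace the 90% with two-sided 5% power for 2.85 days at the follow-up achieved, naming the SD in each arm and any R-squared assumed for covariates or auxiliary variables. For example: with x% of randomised patients followed up, SDs of a and b, and R-squared r, power is y%.

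Use the follow-up rate pooled over both arms. Recruitment ended on 5 April 2019, so 6-month follow-up should have been essentially complete by about October 2019. The SAP is dated 4 December 2019, and analysis was to start in January 2020. The pooled rate should therefore be available without comparing the arms.

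Do not enrol more patients. The cost is one sentence and one recalculation, best made together with the correction for sidedness. The downside is that the stated power will probably be less favourable.

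### The power sentence gives the significance level as 0.05% instead of 5%, and the 90% power beside it does not fit the SAP's two-sided 0.05 test

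*SAP*

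**What the plan says.** Three places in the SAP give a significance level.

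- **Statistical analyses and sample size, opening paragraph:** "A two-sided alternative will be used with a significance level of" 0.05. This describes how the outcome models will be tested.
- **Level of confidence and p values:** "A confidence level of 95% and *p* value of 0.05 is assigned". This agrees with the first.
- **Power calculation, last sentence:** the sample size is derived "using a 0.05% level of statistical significance".

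The last sentence also carries the sample size, "a total sample of 200 patients in each group is needed", and the power claim: this number "is needed to have 90% power of detection a difference of this magnitude". The difference is half of 5.7 days ("days, i.e. a reduction of 2.85 days"), and the SD of 9.7 is assumed equal in both groups. The sentence does not say whether the calculation was one-sided or two-sided. It refers to Figure 2, which is not available here.

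**The concern.** A sample-size statement rests on five inputs: difference, SD, power, type I error and sidedness. Here the type I error is printed as 0.0005, which disagrees with the 0.05 given elsewhere in the SAP, and the sidedness is not given. A reader who tries to reproduce 200 per group from the sentence as it stands will fail by a wide margin.

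What is at stake is whether the power claim can be checked. As long as the level is wrong and the sidedness is unstated, it is easy to miss that the claimed 90% does not belong to the two-sided test the SAP plans to run.

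**Working it through.** **Inputs (SAP, Power calculation):** difference d = 5.7 − 2.85 = 2.85 days; SD = 9.7 in each group; n = 200 per group; target power 90%. No allowance for dropout is stated, so none is applied.

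**Formulas (normal approximation, equal groups):**

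- SE = SD × √(2/n) = 9.7 × √(2/200) = 0.97 days, so d/SE = 2.85/0.97 = 2.938
- Power = Φ(d/SE − z), where z is the critical value
- n per group for 90% power = 2 × (SD/d)² × (z + 1.282)², with 2 × (9.7/2.85)² = 23.17

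**Which level reproduces 200 per group with 90% power?**

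| Level | Sides | z | Power at 200 per group | n per group for 90% |
|---|---|---|---|---|
| 0.0005 (as printed) | two | 3.481 | Φ(−0.543) = 29.4% | 526 |
| 0.0005 (as printed) | one | 3.291 | Φ(−0.352) = 36.2% | 485 |
| 0.05 | two | 1.960 | Φ(0.978) = 83.6% | 244 |
| 0.05 | one | 1.645 | Φ(1.293) = 90.2% | 199 |

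Only the last row reproduces the SAP's figure. Exact t-test calculations agree closely: 28.6% for two-sided 0.0005, 83.4% for two-sided 0.05 and 90.1% for one-sided 0.05.

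**The same result in days.** At two-sided 0.0005, an observed difference would have to reach 3.481 × 0.97 = 3.38 days to be significant. That exceeds the 2.85 days the trial is sized to detect. At two-sided 0.05 the figure is 1.960 × 0.97 = 1.90 days. A calculation aiming for 90% power cannot have used a level at which the target difference itself falls short of significance.

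**Level implied by the stated n and power.** z = 2.938 − 1.282 = 1.657, which is a one-sided level of about 0.049 or a two-sided level of about 0.098. The printed 0.0005 is nowhere near either.

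**The case against.** The strongest reply is that this is a slip in one figure. The SAP fixes the threshold for its tests twice, both times at 0.05, and the power sentence only describes how the sample size was reached. Since 0.0005 is arithmetically impossible for 200 per group and 90% power, and 0.05 is the only other level in the document, nobody following the SAP would test at 0.0005. Recruitment had also ended (5 April 2019, with 401 enrolled) before the SAP was dated (4 December 2019), so the correction changes neither the sample size nor the analysis.

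Most of this stands. A reader might infer that the SAP carries two rival decision thresholds, or that a result at the 2.85-day target could be declared non-significant. The documents support neither: the power sentence sets no rule for judging results, and the 3.38-day hurdle belongs to a level that was evidently never used. Nor do the 29% and 526 per group describe the trial's real power or a real shortfall. They show only that the printed level is wrong.

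The reply does not settle the sidedness. Once the level is read as 5%, 200 per group has 90% power for a one-sided test but not for the two-sided test the SAP specifies. Figure 2 may state the settings used, but it could not make the printed level correct.

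**Conclusion.** The power sentence misstates the type I error by a factor of 100 (0.05/0.0005) and contradicts the SAP's own analysis level. The analysis threshold is consistently 0.05 and is not affected.

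As printed, the power claim is false: about 29% rather than 90%. With the level corrected to 5% and the test two-sided as planned, 200 per group gives about 84%.

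These figures assume the SAP's difference of 2.85 days, a common SD of 9.7, a simple comparison of two means and complete follow-up. Loss to follow-up would lower the power. Covariate adjustment might recover some, but the SAP gives no figure from which to quantify it. That the calculation was one-sided is an inference from the arithmetic, because the SAP does not say so.

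This is a minor correction.

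**What to change.** In the last sentence of the Power calculation:

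1. Replace the printed level with 5% (0.05).
2. State the sidedness actually used to reach 200 per group.
3. Do not leave 90% power attached to a two-sided 5% test. For that test, state that 200 per group gives about 84% power for a difference of 2.85 days with SD 9.7, before any loss to follow-up. If the calculation was one-sided, say so and give the two-sided figure beside it.

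Inserting only the words two-sided 5% and keeping 90% would replace one false statement with another.

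The cost is an edit to one sentence. No patients, data or analyses are added, and the planned tests stay as they are. The drawback is that the reported power falls from 90% to about 84%.

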Statistical Analysis Plan for The Self-Match Study: a randomized controlled trial to assess if treatment outcome is improved if patients match themselves to treatment options

[name]^{1,2,3}, [name]^{1,2,3} and [name]^{1,2,3}.

¹Institute of Clinical Research, Unit of Clinical Alcohol Research (UCAR), University of Southern Denmark, Odense, Denmark

²OPEN, Odense Patient data Explorative Network, Odense University Hospital, Odense, Denmark.

³Psychiatric Research Unit, Region of Southern Denmark.

Contact information:

[name] (Corresponding author): [contact]

[name]: [contact]

[name]: [contact]

ClinicalTrial.gov identifier: NCT03278821. Document date: December 4, 2019.

Abstract

Background: There is growing emphasis on involving patients in their own treatment, however, research has been limited on the benefit of having patients choose their treatment from among options, in contrast to being assigned to a treatment by experts. Consequently, we designed a rigorous test of patient self-matching to determine whether it does improve retention, adherence and outcome in alcoholism treatment.

Method: The present study is conducted as a superiority randomized controlled trial. 401 consecutive patients aged 18 or more is enrolled and randomized to either self-matching or expert-matching to one of five different treatment approaches. The following instruments was administered at intake to provide standardized measures of alcohol problems: Addiction Severity Index, Time Line Follow Back, WHO quality of life questionnaire, NEO Five-Factor inventory-3 and Personal Happiness Form. Methods of statistical analysis are described, including the handling of missing data.

Outcome: For each outcome measure, two analyses will be conducted. Intention-to-treat analyses (ITT) will be carried out with all patients, irrespective of whether they completed the interventions or were re-interviewed. Regarding incomplete data, multiple imputations will be used together with ITT. Completer analyses will also be carried out with patients who complete their respective interventions.

Primary outcome: Decrease in number of monthly excessive drinking days 6 months after initiation of treatment.

Secondary outcomes: (1) Compliance. (2) Quality of life.

Trial registration: ClinicalTrial.gov identifier: NCT03278821. Registered September 12, 2017

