Number of drinking days last 30 days			
Overall alcohol consumption last 30 days			
Retention			
Compliance (drop out)			
Average number of sessions completed			
Quality of Life			

Physical domain (sum score)
Psychological domain (sum score)
Social domain (sum score)
Environment domain (sum score)

Table 3: Treatment success of selfmatch compared to expert match. Treatment success defined as 50% reduction in heavy drinking days.

	Heavy drinking days		Number of drinking days		Overall consumption		Compliance (drop out)		Number of sessions completed		QoL physical domain		QoL psychological domain		QoL social domain		QoL environment domain	
	OR	CI	β	CI	β	CI	β	CI	β	CI	β	CI	β	CI	β	CI	β	CI
Expert-match																		
Self-match																		
Intercept																		

Trial status

The second version of the protocol was accepted the 17th of November 2016. The study was accepted by the Regional Scientific Ethical Committee for Southern Denmark the 24th of March 2017. Recruitment began 22nd of May 2017 ended the 5th of April 2019.

Trial registration: ClinicalTrial.gov identifier: NCT03278821

Declarations

Ethics approval and consent to participate

The Study was presented for the Regional Scientific Ethical Committee for Southern Denmark, who decided that the study did not need formal approval from the committee. Reference number: S-20170027. All procedures in the study are in accordance with the second Declaration of Helsinki.

Both oral and written information will be given to patients by the person who undertakes first baseline interview. Patients must sign informed consent document if they want to participate in the study.

All appointments in Center for Alcohol Treatment Odense are situated in private rooms with quiet and calm atmosphere and there will be no interruptions.

Availability of data and materials

All data collected in the study will be treated and stored strictly confidentially in REDCAP, OPEN. The datasets generated and/or analyzed during the current study are available from the corresponding author on reasonable request.

Competing interests

[name] (PI), [name] and [name] are employees of the University of Southern Denmark and Region of Southern Denmark. [name] is employed at the psychiatry of Region Syddanmark. None of researchers have competing interests to declare.

Funding

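### Table 3 gives the primary outcome's only effect estimate as an odds ratio that no planned model yields, and the fallback quantile and deciding analysis are not stated

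*SAP*

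**What the plan says.** **Outcome.** Under Outcome measures the primary outcome is "Number of excessive drinking days 6 months after initiation of treatment". The abstract words it as "Decrease in number of monthly excessive drinking days 6 months after initiation of treatment". Hypothesis 1 speaks of "significantly greater reductions in alcohol consumption (measured by number of days with excessive drinking) at follow-up".

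**Model.** Statistical analyses and sample size states: "A multiple regression model will be used to model percent of days with drinking/excessive drinking". If the data are too far from normal, "a multiple quantile regression model will be used instead". No quantile is named, and no criterion for the switch. Problem severity is among the explanatory variables, but baseline excessive drinking days are not named.

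**Sample size.** "The power calculation is based on the number of days with excessive alcohol abuse over the last 30 days after 6 months of treatment". The comparison is between arms: a mean of 5.7 days against 2.85, SD 9.7 in both, 200 per group, 90% power.

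**Shells.** Table 2 has a row for heavy drinking days, a column per arm and a significance level, but no effect estimate or interval. Table 3 has estimates with intervals. Its title reads "Treatment success defined as 50% reduction in heavy drinking days", its heavy-drinking column is headed OR, and every other column is headed β.

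**Analysis sets.** Each outcome gets an ITT analysis, with multiple imputation, and a completer analysis. Retention, measured by sessions attended, is a secondary outcome.

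**The concern.** I read heavy and excessive drinking days as the same measure. The one place where the primary variable is given an effect size and interval then belongs to a different analysis from the one the text plans and powers. Neither Gaussian nor quantile regression gives an odds ratio, and no logistic or other binary model appears in the SAP. An analyst who fills in the shells must invent that model, choose what the 50% is measured from, and decide how to class patients with no heavy drinking days at baseline. The estimate that the sample size supports would appear only as two arm summaries and a p value.

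The fallback adds a second open choice. If it is triggered, the powered mean difference is no longer estimated, and the quantile that replaces it could be picked after the data are seen.

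Finally, no sentence says that the ITT result decides if ITT and completer results disagree.

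**Working it through.** **1. What the sample size was built on.** Inputs from Power calculation: difference 2.85, SD 9.7. Formula: n per arm = 2 × (9.7/2.85)² × (z_α + 1.2816)².
- Two-sided 5% (z_α = 1.960): 243.4, so 244 per arm; 200 per arm gives 83.6% power.
- One-sided 5% (z_α = 1.645): 198.4, so 199 per arm; 200 per arm gives 90.2% power.

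The stated 200 matches the one-sided calculation although the SAP sets a two-sided test. That is a separate matter. What counts here is that the figure comes from a difference in mean days, so it says nothing about an odds ratio.

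**2. The two halvings differ.** Power calculation halves the mean of one arm relative to the other (5.7/2 = 2.85). Table 3's 50% reduction most naturally reads as a change within a patient. The first gives no support to the second.

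**3. What the odds ratio would need.** Control response rates are assumed; the SAP gives none. Formula: n = [1.960 × √(2p̄(1−p̄)) + 1.2816 × √(p₁(1−p₁) + p₂(1−p₂))]² / (p₂−p₁)², with n = 200 and two-sided 5%. Example: p₁ = 0.60, p₂ = 0.751, p̄ = 0.6755 gives (1.298 + 0.838)² / 0.151² ≈ 200.

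| Assumed control rate | Detectable difference, points | OR |
|---|---|---|
| 40% | 16.1 | 1.92 |
| 50% | 15.9 | 1.93 |
| 60% | 15.1 | 2.01 |
| 70% | 13.6 | 2.19 |
| 80% | 11.3 | 2.63 |

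If dropping patients with zero baseline days left 160 per arm (assumed), the range is 12.4 to 18.0 points.

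**4. What the fallback would estimate.** Inputs: 0–30 days, control mean 5.7, SD 9.7. The shapes, and SDs of 6 to 8 at mean 2.85, are assumed.
- *Beta-binomial.* Control: m = 5.7/30 = 0.19; ρ = (94.09/(30 × 0.19 × 0.81) − 1)/29 = 0.668. This gives 58.7% zeros, median 0, 75th percentile 7, 90th percentile 25. At mean 2.85 the median is 0, the 75th percentile 0 to 2 and the 90th 11 to 12. Unadjusted contrasts are 0, 5–7 and 13–14 days.
- *Negative binomial.* Control: k = 5.7²/(94.09 − 5.7) = 0.368. This gives 35.7% zeros, median 2, 75th percentile 7, 90th percentile 17. At mean 2.85 the values are 0, 2–3 and 8–9. Contrasts are 2, 4–5 and 8–9 days. This shape puts about 3% of control patients above 30 days.
- *No shape assumed.* The second moment must be 94.09 + 5.7² = 126.6. With half the patients at 0, a share p at 30 and the rest at the median M, p = (5.7 − 0.5M)/(30 − M). The largest second moment is 133.8 at M = 4 and 124.5 at M = 5, so the median cannot exceed 4.

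**5. The three wordings.** Let Y be the 6-month count, B the baseline count and T the arm. If Y = α + βT + γB + error, then B − Y = −α − βT + (1−γ)B + error. The treatment coefficient is the same apart from sign. Percent of 30 days multiplies it by 100/30.

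**6. Completers and retention.** Completers are selected after randomisation by having stayed in treatment. Retention measures staying in treatment. Restricting to completers therefore conditions on the outcome being compared.

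**The case against.** Much of this is settled on a fair reading. Outcome measures names the count as primary, hypothesis 1 uses it and the sample size rests on it; the responder definition appears only in a table title. A reader might infer that the SAP has two rival primary outcomes, or that its error rate is inflated because either could be claimed. The text does not support that: it nowhere ranks the responder beside the count and states no rule under which either would suffice.

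Table 2 does report and test the count, so it would be wrong to say that the count goes unreported. Table 3's headings may also be loose: drop-out, which looks binary, is headed β. A labelling slip is plausible, but the title defines success explicitly, so the shell needs correcting either way.

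The three wordings might be read as three different outcomes. Step 5 shows that they are not once baseline is adjusted for.

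ITT comes first, covers all patients and carries the imputation plan, and complete-case computation is listed as a sensitivity analysis. That points to ITT as the main analysis, and only the statement is missing.

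The quantile contrasts depend on the assumed shape and are unadjusted, so a zero contrast at the median is not established. What stands is that the answer varies widely with an unnamed quantile.

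**Conclusion.** The point holds in a limited form and should be corrected before analysis. The primary variable's only planned effect estimate with an interval is an odds ratio without a model, reference point, zero-baseline rule, status or power, while the powered mean difference has arm columns and a significance level only. The fallback could replace that mean difference with a contrast anywhere from 0 to 14 days in the assumed examples, depending on the quantile. The priority of ITT is implied but not stated, and a completer analysis of retention cannot support inference.

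The contradiction between Table 3 and the model section rests on the SAP's text alone, given that heavy and excessive drinking days are the same measure. The sizes rest on assumed response rates, distribution shapes and SDs and are illustrative. Which variable is primary is not seriously in doubt.

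**What to change.** - **Table 3:** change the heavy-drinking column to β (difference in mean days) with 95% CI.
- **Deciding analysis:** state that hypothesis 1 is decided by the ITT analysis, with multiple imputation, of the number of excessive drinking days in the last 30 days at 6 months, adjusted for baseline heavy drinking days. Align the wording in the abstract and the model section.
- **Non-normality:** keep the mean difference as the deciding estimate, with robust or bootstrap standard errors if residuals are non-normal. Make quantile regression a sensitivity analysis with the quantile named. At minimum, fix the quantile and the trigger before the data are seen.
- **Responder odds ratio:** report it as supportive, with its logistic model, baseline reference and zero-baseline rule stated.
- **Completers:** label these analyses supportive and draw no inference on retention from them.

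The cost is SAP and shell wording, to be settled before the January 2020 analysis start. Baseline heavy drinking days are already in Table 1. The downside is that the responder, quantile and completer results lose any deciding status.
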